CRF Case Report Form CTCAE Common Terminology Criteria for Adverse Events DOAC Direct oral anticoagulant EP Extended Prophylaxis HIPAA Health Insurance Portability and Accountability Act IRB Institutional Review Board ITT Intention-To-Treat NIH National Institute of Health NSQIP National Surgical Quality Improvement Program PDC Proportion of Days Covered PE Pulmonary Embolism PI Principal Investigator PMAS PROMIS Medication Adherence Scale POD Post operative day PROMIS Patient-Reported Outcomes Measurement Information System PMAS PROMIS Medication Adherence Scale RC Radical Cystectomy	COST	Comprehensive Score for Financial Toxicity
CTCAE Common Terminology Criteria for Adverse Events DOAC Direct oral anticoagulant EP Extended Prophylaxis HIPAA Health Insurance Portability and Accountability Act IRB Institutional Review Board ITT Intention-To-Treat NIH National Institute of Health NSQIP National Surgical Quality Improvement Program PDC Proportion of Days Covered PE Pulmonary Embolism PI Principal Investigator PMAS PROMIS Medication Adherence Scale POD Post operative day PROMIS Patient-Reported Outcomes Measurement Information System PMAS PROMIS Medication Adherence Scale RC Radical Cystectomy	CrCl	Creatinine Clearance
DOAC Direct oral anticoagulant EP Extended Prophylaxis HIPAA Health Insurance Portability and Accountability Act IRB Institutional Review Board ITT Intention-To-Treat NIH National Institute of Health NSQIP National Surgical Quality Improvement Program PDC Proportion of Days Covered PE Pulmonary Embolism PI Principal Investigator PMAS PROMIS Medication Adherence Scale POD Post operative day PROMIS Patient-Reported Outcomes Measurement Information System PMAS PROMIS Medication Adherence Scale RC Radical Cystectomy	CRF	Case Report Form
EP Extended Prophylaxis HIPAA Health Insurance Portability and Accountability Act IRB Institutional Review Board ITT Intention-To-Treat NIH National Institute of Health NSQIP National Surgical Quality Improvement Program PDC Proportion of Days Covered PE Pulmonary Embolism PI Principal Investigator PMAS PROMIS Medication Adherence Scale POD Post operative day PROMIS Patient-Reported Outcomes Measurement Information System PMAS PROMIS Medication Adherence Scale RC Radical Cystectomy	CTCAE	Common Terminology Criteria for Adverse Events
HIPAA Health Insurance Portability and Accountability Act IRB Institutional Review Board ITT Intention-To-Treat NIH National Institute of Health NSQIP National Surgical Quality Improvement Program PDC Proportion of Days Covered PE Pulmonary Embolism PI Principal Investigator PMAS PROMIS Medication Adherence Scale POD Post operative day PROMIS Patient-Reported Outcomes Measurement Information System PMAS PROMIS Medication Adherence Scale RC Radical Cystectomy	DOAC	Direct oral anticoagulant
IRB Institutional Review Board ITT Intention-To-Treat NIH National Institute of Health NSQIP National Surgical Quality Improvement Program PDC Proportion of Days Covered PE Pulmonary Embolism PI Principal Investigator PMAS PROMIS Medication Adherence Scale POD Post operative day PROMIS Patient-Reported Outcomes Measurement Information System PMAS PROMIS Medication Adherence Scale RC Radical Cystectomy	EP	Extended Prophylaxis
ITT Intention-To-Treat NIH National Institute of Health NSQIP National Surgical Quality Improvement Program PDC Proportion of Days Covered PE Pulmonary Embolism PI Principal Investigator PMAS PROMIS Medication Adherence Scale POD Post operative day PROMIS Patient-Reported Outcomes Measurement Information System PMAS PROMIS Medication Adherence Scale RC Radical Cystectomy	HIPAA	Health Insurance Portability and Accountability Act
NIH National Institute of Health NSQIP National Surgical Quality Improvement Program PDC Proportion of Days Covered PE Pulmonary Embolism PI Principal Investigator PMAS PROMIS Medication Adherence Scale POD Post operative day PROMIS Patient-Reported Outcomes Measurement Information System PMAS PROMIS Medication Adherence Scale RC Radical Cystectomy	IRB	Institutional Review Board
NSQIP National Surgical Quality Improvement Program PDC Proportion of Days Covered PE Pulmonary Embolism PI Principal Investigator PMAS PROMIS Medication Adherence Scale POD Post operative day PROMIS Patient-Reported Outcomes Measurement Information System PMAS PROMIS Medication Adherence Scale RC Radical Cystectomy	ITT	Intention-To-Treat
PDC Proportion of Days Covered PE Pulmonary Embolism PI Principal Investigator PMAS PROMIS Medication Adherence Scale POD Post operative day PROMIS Patient-Reported Outcomes Measurement Information System PMAS PROMIS Medication Adherence Scale RC Radical Cystectomy	NIH	National Institute of Health
PE Pulmonary Embolism PI Principal Investigator PMAS PROMIS Medication Adherence Scale POD Post operative day PROMIS Patient-Reported Outcomes Measurement Information System PMAS PROMIS Medication Adherence Scale RC Radical Cystectomy	NSQIP	National Surgical Quality Improvement Program
PI Principal Investigator PMAS PROMIS Medication Adherence Scale POD Post operative day PROMIS Patient-Reported Outcomes Measurement Information System PMAS PROMIS Medication Adherence Scale RC Radical Cystectomy	PDC	Proportion of Days Covered
PMAS PROMIS Medication Adherence Scale POD Post operative day PROMIS Patient-Reported Outcomes Measurement Information System PMAS PROMIS Medication Adherence Scale RC Radical Cystectomy	PE	Pulmonary Embolism
POD Post operative day PROMIS Patient-Reported Outcomes Measurement Information System PMAS PROMIS Medication Adherence Scale RC Radical Cystectomy	PI	Principal Investigator
PROMIS Patient-Reported Outcomes Measurement Information System PMAS PROMIS Medication Adherence Scale RC Radical Cystectomy	PMAS	PROMIS Medication Adherence Scale
PMAS PROMIS Medication Adherence Scale RC Radical Cystectomy	POD	Post operative day
RC Radical Cystectomy	PROMIS	Patient-Reported Outcomes Measurement Information System
2 2	PMAS	PROMIS Medication Adherence Scale
	RC	Radical Cystectomy
SQH Subcutaneous heparin	SQH	Subcutaneous heparin
SUO Society of Urologic Oncology	SUO	Society of Urologic Oncology
US United States	US	United States
VTE Venous thromboembolism	VTE	Venous thromboembolism

STUDY SUMMARY

1.1 Synopsis

Title: Comparison of Apixaban versus Enoxaparin for VTE Prevention after

Radical Cystectomy (the CARE trial)

Short Title: Comparison of Apixaban versus Enoxaparin (CARE)

Study Description:

Patients who have undergone radical cystectomy for bladder cancer will be randomized to receive a prescription for either enoxaparin or apixaban to self-administer at home until post operative day 30. Their adherence to the assigned medication will be the primary outcome. Comparisons of patient satisfaction, barriers to adherence, and cost will also be collected. The hypothesis is that adherence, satisfaction, and cost will be greater in the apixaban arm.

Objectives:

1. To compare rates of adherence to discharge on enoxaparin vs apixaban

a. Hypothesis: The apixaban group will exhibit non-inferior adherence, as measured by the proportion of prescribed medication accurately administered.

2. To compare costs of discharge on enoxaparin vs apixaban

a. Hypothesis: The median patient out-of-pocket cost, obtained from the institution's outpatient pharmacy data, is expected to be higher in the apixaban group compared to enoxaparin group.

3. To explore factors contributing to EP adherence

a. Hypothesis: it is anticipated that barriers to adherence to enoxaparin will primarily manifest as operational challenges and patient dissatisfaction, while for apixaban, they will predominantly arise from lack of insurance coverage and cost considerations. To evaluate these barriers, a combination of validated questionnaires and novel measures will be employed.

4. To collect safety and efficacy data on enoxaparin and apixaban

a. Considering that our study size will limit statistical power to detect risk reduction in venous thromboembolism (VTE) and/or bleeding events in either enoxaparin or apixaban, we will instead closely monitor and assess VTE and bleeding events in both treatment arms to contribute to existing studies for possible meta-analysis. This will be achieved

through the implementation of screening questions at each visit.

Primary Endpoint:

To address our primary objective, adherence, the primary endpoint will be measured as the proportion of days covered (PDC), ie the proportion of days between discharge and post operative day 30 during which the participant took their anticoagulant as prescribed.

Secondary Endpoints:

To address our secondary objective of comparing risk factors for adherence/non-adherence, secondary endpoints include:

- National Institute of Health (NIH) Patient-Reported Outcomes
 Measurement Information System (PROMIS) Medication
 Adherence Scale (PMAS) a validated, nine-item, patient-reported
 measure of medication adherence¹
- 2. Patient Satisfaction a series of independent questions that investigate barriers to adherence specific to apixaban or enoxaparin

To address our secondary objective of comparing cost, secondary endpoints also include:

- 3. Patient out of pocket cost for anticoagulant prescription (in dollars)
- 4. COST-FACIT, a 12-item survey developed and validated in the cancer population for assessing patient-reported financial distress due to healthcare costs²

Study Population:

Inclusion Criteria: All patients undergoing RC with urinary diversion and pelvic lymph node dissection for urothelial bladder cancer (any T stage, N0-1, M0) at the participating institutions.

Exclusion Criteria:

- 1. Preoperative use of a therapeutic dose of anticoagulant (this notably does *not* exclude patients taking antiplatelet agents)
- 2. Failure to undergo radical cystectomy with concurrent urinary diversion and pelvic lymph node dissection
- 3. Failure to be discharged by POD14
- 4. Failure to be discharged on prophylactic enoxaparin or apixaban.
- 5. Any medical condition which precludes treatment with *either* enoxaparin *or* apixaban (including dialysis,hemophilia, or any other bleeding diathesis)
- 6. Inability to communicate over the phone in English

Due to the natural history of bladder cancer, the expected population will be mixed in age, race, gender, and general health status, though likely to be majority white males between the ages of 50-80 in generally good health status (enough that they are safe to undergo RC, which is a major surgery).

Target sample size is 108 participants

Enrolling Sites: Hospital of the University of Pennsylvania (HUP), Philadelphia, PA

Vanderbilt University Medical Center, Nashville, TN

Description of Study Intervention:

Enoxaparin and apixaban are both established treatments in clinical practice and considered acceptable standards of care. However, enoxaparin has historically been utilized for extended prophylaxis prior to the availability of apixaban and is slightly more commonly prescribed. Hence, in this study, randomization to apixaban will be considered the intervention for convention.

Enoxaparin is taken by subcutaneous injection 40 mg once daily for VTE prophylaxis. Apixaban is taken orally as a tablet at a 2.5 mg twice daily for VTE prophylaxis.

Study Duration: 30 months

Participant Duration:

From preoperative clinic visit to 90 days postop, approximately 4 months

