2.3 Preliminary Institutional Results

Given the earlier data suggesting barriers to adoption include cost, we sought to assess the state of prescription costs at our institution and determine how likely this is to pose a barrier to patient adherence. We reviewed our institution's outpatient pharmacy data from July to December of 2022, including the copays that patients being discharged on prophylactic dose apixaban and enoxaparin face at our institution as well as difficulties encountered with prior authorizations. Data suggest that copays may vary from as low as \$0 to >\$100, and that copays are much more likely to be increased with apixaban (Table 1). Review of prior authorizations show that a substantial number of prior authorizations were submitted, and in particular that denial of these prior authorizations and insurance coverage may pose a problem for both medications, in particular apixaban (Table 2).

Table 1. Patient copays for Enoxaparin and Apixaban

Lovenox PX (30mg & 40mg QD	
Copay (\$)	Count
0	103
0-20	108
21-50	27
51-100	14
>100	17
Total	269

Apixaban PX (2.5mg BID)		
Copay (\$)	Count	
0	15	
0-20	14	
21-50	11	
51-100	3	
>100	4	
Total	47	

Table 2. Outcomes of prior authorizations submitted for Enoxaparin and Apixaban

Prior Authorizations					
Medication	Approved	Denied	Total		
Apixaban	32	9	41		
Lovenox	19	2	21		

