4.1 Minimizing Bias

Patients will be randomized to a prescription for one of the two anticoagulants at the time of postoperative discharge, and instructed to continue the medication until POD30. Randomization will be performed in a simple 1:1 fashion.

The randomization will be non-blinded. Given that this trial aims to explore the real experience of patients on these medications, blinding and placebo would actually detract from the important clinical context and understanding that participants have. Furthermore, enoxaparin and apixaban have different routes of administration (enoxaparin is injectable and apixaban is oral) which makes blinding and placebo infeasible. Blinding of the investigators is not necessary given the outcomes are patient reported surveys and pill/vial counts. Bias will be sufficiently reduced by randomization.

The University of Pennsylvania will serve as the primary site, and Vanderbilt University Medical Center as a second site. The addition of a second site will also introduce variety into the study population and strengthen its applicability.

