7 STUDY ASSESSMENTS

At the time of enrollment, participants will be offered to complete the Demographics questionnaire either in person (if applicable), via phone (if applicable), or via a secure REDCap link emailed to them.

Participants will be contacted via phone on POD30 and POD90. During the phone call, participants will be given the option to receive an email with a secure link to REDCap to complete the majority of the study visit electronically (PMAS, Patient Satisfaction, and COST

questionnaires). Medication counting and screening for adverse events including VTE and bleeding must be done over the phone rather than via emailed link.

Study assessments will be conducted by staff other than the treating physician, and staff members will clearly state the contact is part of the research study, not part of routine clinical care.

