9 STATISTICAL CONSIDERATIONS

9.1 General Approach

Continuous variables will be presented as means with standard deviation or median with interquartile range. All statistical tests of significance will be two-sided with alpha level 0.05. Stata will be used for all statistical analysis.

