9.4 Analysis of Secondary Endpoints

The following secondary endpoints will be assessed to further characterize adherence and also related elements of satisfaction and cost, though analyses of these related elements are not dependent on findings of the primary endpoint.

- 1. A binary measure of adherence: adherent vs non-adherent. Adherent is defined as taking *all* intended anticoagulant. Adherence in this definition will be compared using a test of proportions (proportion of patients in one study arm that were "adherent" vs proportion of patients in the other arm that were "adherent") within the ITT and population.
- 2. Cost of the medication. There are several measures of cost that will be studied as endpoints, including overall medication cost, cost paid by insurance, and most importantly participant out of pocket cost. Cost will be measured in dollars and reported as median and as mean depending on the presence of outliers. This will be collected from pharmacy review of prescriptions. Cost will be compared using a rank sum test.
- 3. Scores on the two validated questionnaires given: PROMIS and COST. These validated questionnaires both have scoring systems and a t test of the average score of participants in each arm will be compared (ie average score on COST for participants in apixaban arm vs average score on COST for participants in enoxaparin arm). A rank sum test will be used if distributions have outliers.

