9.5 Exploratory Analysis

Analysis of other factors influencing adherence to at home anticoagulation in this population are considered exploratory. To explore what factors other than type of anticoagulant may be impacting adherence, we plan to perform a logistic regression with the outcome variable of PDC. Covariates will include the following: age, gender, ethnicity, marital status, living situation, occupational status, education level, annual household income, insurance status, history of prior blood clot, number of daily medications, discharge destination, study arm, and items from the Satisfaction Questionnaire. Univariate regression will be performed first followed by multivariate regression including all variables that were significantly associated on univariate regression.

A second exploratory analysis will be comparing elements of the novel satisfaction questionnaire trial between the apixaban and enoxaparin arms. Items from this questionnaire may be compared by presenting descriptive statistics without formal tests for statistical significance in order to explore how patient satisfaction varies between the study arms and allow future physicians to give anticipatory guidance.

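### The out-of-pocket cost test (9.4 item 2) is valid but takes no account of site and insurance status; prespecify an adjusted rank-based comparison, for an assumption-dependent gain in power

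*Combined protocol and SAP*

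**What the plan says.** The Synopsis (1.1, Objective 2) states a directional hypothesis: median patient out-of-pocket cost "is expected to be higher in the apixaban group compared to enoxaparin group". Section 9.4 item 2 lists several cost measures, singles out the participant's own payment as the one that matters most, and gives one method: "Cost will be compared using a rank sum test". It names no strata or covariates. Section 9.1 sets the level: "All statistical tests of significance will be two-sided with alpha level 0.05".

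On design, 4.1 says "Randomization will be performed in a simple 1:1 fashion" and names two sites. The time of allocation is also in 4.1: "Patients will be randomized to a prescription for one of the two anticoagulants at the time of postoperative discharge". Section 7 says "At the time of enrollment, participants will be offered to complete the Demographics questionnaire", and 5.3 requires enrolment before surgery. Section 7.3 describes that questionnaire as the source of sociodemographic covariates but does not list its items. The covariate list in 9.5 includes "annual household income, insurance status", but that regression has adherence (PDC) as its outcome. Section 9.7 runs the cost analyses on all prescriptions, possibly more than one per participant.

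**The concern.** Participants fill the prescription at their own cost (section 6). The protocol itself treats insurance as a driver of access and expense: Objective 3 expects the barriers to apixaban to come from coverage and cost, and 2.3 reports prior-authorisation denials of 9 of 41 for apixaban and 2 of 21 for enoxaparin. It is therefore odd to use insurance status to explain adherence but not to sharpen the cost comparison.

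Table 1 shows a wide spread of copays within each drug and a modest shift between drugs. If part of that spread belongs to insurer or site, a plain rank sum test counts it as noise, and a real difference in out-of-pocket cost is more likely to be reported as no difference. Adjustment added after the data are seen would look data-driven, so the decision belongs in the plan now.

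**Working it through.** **Stated figure.** The plan gives no power or sample size for cost. The 45 per arm (90 analysed, 108 enrolled; 5.3 and 9.3.1) was set for PDC and is taken here as given.

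**Effect implied by Table 1 (2.3).** Bands are $0, 0-20, 21-50, 51-100 and over 100.
- Enoxaparin: 103, 108, 27, 14, 17 of 269, or shares 0.383, 0.401, 0.100, 0.052, 0.063.
- Apixaban: 15, 14, 11, 3, 4 of 47, or shares 0.319, 0.298, 0.234, 0.064, 0.085.
- Copay above $20: enoxaparin 58/269 = 21.6%; apixaban 18/47 = 38.3%.
- Cumulative share through the 0-20 band: enoxaparin 211/269 = 78.4%; apixaban 29/47 = 61.7%. Both medians lie in that band.
- P(apixaban copay higher) plus half of ties = sum over bands of the apixaban share × (enoxaparin share below + half the enoxaparin share in the band) = 0.319×0.191 + 0.298×0.584 + 0.234×0.835 + 0.064×0.911 + 0.085×0.968 = 0.571.

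**Simulation.** There are 45 per arm, and each test is two-sided at 0.05. Each participant has a normal latent cost, cut into bands so that each arm reproduces its Table 1 shares. A share R² of the latent variance is due to insurance and site. The documents do not give R², so it is varied. Further assumptions are four insurance groups in a 50/30/15/5% mix, R² split 70:30 between insurance and site, and a site mix of 70:90 from the annual volumes in 5.3.

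Three tests are compared:
1. Plain rank sum: z = (W − n₁(N+1)/2)/√V, with V = n₁n₀/(N(N−1)) × Σ(r − r̄)², using midranks for ties.
2. Van Elteren over 8 strata (4 insurance groups × 2 sites): the stratum terms W − E, weighted by 1/(n_k+1), divided by the root of the weighted variances.
3. Adjusted ranks (rank ANCOVA): residuals of the ranks and of arm after regression on insurance and site, with z = partial correlation × √df.

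| R² | Plain | Adjusted ranks | Van Elteren |
|---|---|---|---|
| 0 | 23% | 22% | 21% |
| 0.10 | 23% | 24% | 22% |
| 0.20 | 22% | 25% | 23% |
| 0.40 | 23% | 32% | 29% |
| 0.60 | 22% | 39% | 37% |

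A repeat with 4,000 runs per row agreed to within 2 points. The standard error of one entry is about √(0.23×0.77/4000) = 0.7 points, so the 1-point difference at R² = 0.10 is not a gain. With no drug effect, all three tests reject in about 4-6% of runs.

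**Sensitivity.**
- At 54 per arm, plain / adjusted / van Elteren power is 26/32/29% at R² = 0.25 and 27/42/39% at R² = 0.50.
- With a larger assumed shift (0.6 latent SD) and 45 per arm, it is 75/76/73% at R² = 0.10, 75/82/80% at 0.25 and 74/92/91% at 0.50.
- If 10% of insurance answers were missing and those participants were dropped, van Elteren power would be about 19% at R² = 0 and 21% at R² = 0.20, below the plain test. A separate category for missing insurance holds the loss with adjusted ranks to about 1 point.

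**The case against.** The strongest reply is that nothing here is an error. Allocation is simple 1:1, so an unstratified test matches the design and keeps its type I error. Cost is secondary, and no power is claimed for it. That stands. A reader might infer that ignoring insurance and site biases the comparison, or that a chance imbalance in insurance mix invalidates it. The documents do not support this: such imbalance is part of the sampling variation that the test already allows for. The loss is one of efficiency only.

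A reader might also take the spread in Table 1 as proof that insurers or sites cause it. Table 1 cannot show that. It comes from one institution, has no insurer breakdown, pools 30 mg and 40 mg enoxaparin prescriptions, and is not described as limited to cystectomy patients. How much of the spread adjustment would remove is unknown.

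Three practical objections also stand. Van Elteren over eight small strata can lose about 2 points. Recording of insurance status before randomisation is a sound inference from 7, 7.3 and 9.5, but the items are not shown and the questionnaire is only offered. The prescription-level dataset and the discarding of missing data in 9.7 also mean that a change confined to the name of the test would be incomplete. These objections shape the remedy. They do not remove the case for using covariates that the plan already intends to collect.

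**Conclusion.** The point holds as a modest, low-cost gain in efficiency on the cost measure that the plan ranks highest. Under the Table 1 effect with 45 per arm, adjusted ranks raise power from about 22-23% to about 25%, 32% and 39% if insurance and site explain 20%, 40% and 60% of latent copay variance. At 10% or less the gain is nil. The explained share, the insurance mix and the insurance-to-site split are all assumptions.

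It would be tempting to conclude that adjustment rescues the cost objective. It does not: even at 60% explained, the Table 1 effect would be missed in about 61% of trials (100 − 39). Sample size and the small shift between drugs matter more than the missing covariates, and a non-significant cost result should not be read as equal cost under either analysis.

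**What to change.** In 9.4 item 2, prespecify that out-of-pocket cost is compared by randomised arm with a rank-based analysis adjusted for site and a few fixed insurance categories. Either rank ANCOVA or a proportional-odds model will do; both are preferable to van Elteren over many small strata. In addition:
- give missing insurance status its own category, so that no participant with a known cost is dropped, and say so alongside the missing-data rule in 9.7;
- use one out-of-pocket total per participant for this test, and reconcile that with the all-prescriptions dataset in 9.7;
- confirm that insurance status is recorded before randomisation;
- keep the median and interquartile range by arm, with the plain rank sum test as a sensitivity analysis.

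The cost is a few sentences in 9.4 and 9.7 and, if insurance status is recorded as 9.5 implies, no new data. The categories must be fixed in advance. If insurance and site explain nothing, about 1 point of power is lost (about 2 with van Elteren over eight strata).
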